6.4. WINDOWING CONVENTIONS

Unless otherwise specified, visit data as recorded in the database will be used for the analysis. No visit windowing recalculation will be performed for this trial.

Document:	\\ieedc-vnasc01\BIOSdata\Boehringer_Ingelheim\BI_695501\NVA96252\Biostatistics\Documentation\SAP\BI1297.4 SAP FINAL v4.0_22MAY2019.docx		
Author:	Version Number:	Final V4.0	
	Version Date:	22MAY2019	
Template No:	CS_TP_BS016	Revision 5	Reference: CS_WI_BS005
Effective Date:	01Apr2018		

6.5. STATISTICAL TESTS

The default significance level will be 10%; confidence intervals will be 90% and 95% and all tests will be two-sided, unless otherwise specified in the description of the analyses.

6.6. COMMON CALCULATIONS

For quantitative measurements, change from baseline will be calculated as:

- Test Value at Visit X – Baseline Value

6.7. SOFTWARE VERSION

All analyses will be conducted using SAS version 9.4 or higher.

7. STATISTICAL CONSIDERATIONS

7.1. ADJUSTMENTS FOR COVARIATES AND FACTORS TO BE INCLUDED IN ANALYSES

The following covariates and factors are used in the primary and secondary efficacy analyses. For details of their inclusion in the models, see the specific analysis section.

- Treatment (BI 695501 versus EU-approved Humira)
- Prior exposure to infliximab (Yes/No).
- Baseline SES-CD (<16 or ≥16)

7.2. MULTICENTER STUDIES

This trial will be conducted by multiple investigators at multiple centers internationally, approximately 128 clinical sites across approximately 13 countries. Randomization to treatment arms is stratified by prior exposure to infliximab (Yes/No) and screening SES-CD (<16 or ≥16). No stratification by site was planned because of the small number of subjects to be randomized per site.

Document: \\ieedc-
vnasc01\BIOSdata\Boehringer_Ingelheim\BI_695501\NVA96252\Biostatistics\Documentation\S
AP\BI1297.4 SAP FINAL v4.0_22MAY2019.docx

Author: Version Number: Final V4.0
Version Date: 22MAY2019

Template No: CS_TP_BS016 Revision 5
Effective Date: 01Apr2018

Reference: CS_WI_BS005

7.3. MISSING DATA

Missing safety data will not be imputed, unless otherwise specified in section 16.

Missing efficacy data will be handled as described in section 15.

Calculation for a partial date is described in APPENDIX 2.

7.4. MULTIPLE COMPARISONS/ MULTIPLICITY

No multiplicity consideration is required in this trial.

7.5. EXAMINATION OF SUBGROUPS

There is no examination of subgroups.

8. OUTPUT PRESENTATIONS

APPENDIX 1 shows conventions for presentation of data in outputs.

The templates provided with this SAP describe the presentations for this trial and therefore the format and content of the summary tables, figures, and listings to be provided by Biostatistics.

9. DISPOSITION AND WITHDRAWALS

All subjects who provide informed consent will be accounted for in this trial.

The counts of the analysis sets will be presented:

- All Subject Enrolled Set (ENR)
- All Subjects Randomized Set (RND)
- Full Analysis set (FAS)
- Per Protocol Analysis Set (PPS, PPS2)
- Safety Analysis Set (SAF)

Document: \\ieedc-vnasc01\BIOSdata\Boehringer_Ingelheim\BI_695501\NVA96252\Biostatistics\Documentation\SAP\BI1297.4 SAP FINAL v4.0_22MAY2019.docx

Author: Version Number: Final V4.0
Version Date: 22MAY2019

Template No: CS_TP_BS016 Revision 5
Effective Date: 01Apr2018

Reference: CS_WI_BS005

The reasons for exclusion from the analysis sets will be listed.

The following subject disposition and withdrawals will be presented for the ENR set:

- Screened
- Screen failure (defined as withdrawn from trial prior to randomization)
- Primary reason for non-inclusion
- Randomized
- Randomized but not treated
- Treated
- Subjects with CDAI decrease ≥ 70 at Day 29 (Week 4)
- Subjects treated after Day 29 (Week 4)
- Completed treatment at Day 337 (Week 48)
- Completed the trial per the protocol
- Discontinued from treatment strictly before Day 29 (Week 4), primary reason for premature discontinuation from treatment before Day 29 (Week 4)
- Discontinued from treatment (before Week 48), primary reason for premature discontinuation from treatment
- Discontinued from trial (after Week 48), primary reason for premature discontinuation from trial

The following subject disposition and withdrawals will be presented for the ENR set per site:

- Screened
- Screen failure (defined as withdrawn from trial prior to randomization)
- Randomized
- Randomized but not treated

Document: \\ieedc-vnasc01\BIOSdata\Boehringer_Ingelheim\BI_695501\NVA96252\Biostatistics\Documentation\SAP\BI1297.4 SAP FINAL v4.0_22MAY2019.docx

Author: Version Number: Final V4.0
Version Date: 22MAY2019

Template No: CS_TP_BS016 Revision 5
Effective Date: 01Apr2018

Reference: CS_WI_BS005

- Treated
- Subjects with CDAI decrease ≥ 70 at Day 29 (Week 4)
- Subjects treated after Day 29 (Week 4)
- Completed treatment at Day 337 (Week 48)
- Completed the trial (Week 56)

9.1. IMPORTANT PROTOCOL DEVIATIONS

Protocol violations (as defined in section 5.4), as well as inclusion and exclusion criteria violators will be tabulated and listed for the FAS.

Important protocol violations are defined as:

- entering the study even though the subject did not fulfill the entry criteria;
- developing withdrawal criteria during the study but the subject did not withdraw;
- receiving the wrong treatment or incorrect dose;
- receiving a prohibited concomitant treatment.

Important protocol violations confirmed by a clinical and medical review as recorded in the protocol deviations log will be tabulated and listed for the FAS. These violations are not the ones excluding subjects from either one of the PPSs (refer to section 5.4).

The full protocol deviations log will be attached to the clinical trial report.

10. DEMOGRAPHIC AND OTHER BASELINE CHARACTERISTICS

No statistical testing will be carried out for demographic or other baseline characteristics.

The following demographic characteristics will be reported at Primary Analysis for the FAS, PPS and SAF, and at Final Analysis for RND, FAS, PPS, PPS2 and SAF:

- Age (years) at Informed Consent
- Gender (Male/Female)

Document: \\ieedc-vnasc01\BIOSdata\Boehringer_Ingelheim\BI_695501\NVA96252\Biostatistics\Documentation\SAP\BI1297.4 SAP FINAL v4.0_22MAY2019.docx

Author: Version Number: Final V4.0
Version Date: 22MAY2019

Template No: CS_TP_BS016 Revision 5
Effective Date: 01Apr2018

Reference: CS_WI_BS005

Statistical Analysis Plan

- Childbearing potential (Post-Menopausal/Surgically Sterile/Childbearing Potential (tubal ligation at least 6 weeks before screening is considered not of childbearing potential))
- Race (American Indian or Alaska Native/Asian/Black or African American/Native Hawaiian or Other Pacific Islander/White/Other)
- Ethnicity (Hispanic or Latino/Not Hispanic or Latino/Not reported/Unknown)
- Country
- Weight at baseline (kg)
- Height at baseline (cm)
- BMI at baseline (kg/m²)

The randomization stratification categories (Prior exposure to infliximab Yes/No, screening SES-CD <16/≥16) based on eCRF data, will be presented at Primary and Final Analyses for the FAS. Any differences between stratification data in the eCRF and IVRS will be documented.

The following baseline disease characteristics will be presented at Primary Analysis for the FAS, PPS, SAF, and at Final Analysis for FAS, PPS2, and SAF:

- CDAI score at baseline as collected in the eCRF
- Mucosal ulceration at baseline as collected in the SES-CD under the item: Extent of ulcerated surface subscore. The second reading will be taken into account in case there were two readings.

Other baseline characteristics will be presented on FAS and SAF:

- Infection screen (for HBsAg, HCV and HIV test)
- Chest X-Ray result
- Tuberculosis (TB) test
- CRP at baseline
- Fecal calprotectin at baseline

Document: \\ieedc-
vnasc01\BIOSdata\Boehringer_Ingelheim\BI_695501\NVA96252\Biostatistics\Documentation\S
AP\BI1297.4 SAP FINAL v4.0_22MAY2019.docx

Author: Version Number: Final V4.0
Version Date: 22MAY2019

Template No: CS_TP_BS016 Revision 5
Effective Date: 01Apr2018

Reference: CS_WI_BS005

- Stool studies at baseline (*Salmonella*, *Shigella*, *Yersinia*, *Campylobacter*, *Vibrio*, *Escherichia coli* O157/H7, *Clostridium difficile* toxin, Enteric parasites and their ova including *Cryptosporidia*), and other identified pathogens.

Accountability for missing data will be displayed in case of any missing entries.

10.1. DERIVATIONS

- Conversion factors:
 - 1 lbs=0,453592 kg
 - 1 in=2,54 cm
- BMI (kg/m²) = weight (kg)/height (m)²
- Age (years) = (date of consent– date of birth)/365.25

11. SURGICAL AND MEDICAL HISTORY

Surgical and Medical History information will be presented at Primary Analysis for the SAF, and at Final Analysis for the FAS and SAF.

Surgical and Medical History will be coded using MedDRA version 19.1 or higher.

The system organ classes will be sorted by internationally agreed EMA SOC (System Organ Class) order (refer to APPENDIX 3), preferred terms will be sorted by decreasing frequencies (within system organ class).

Data captured on the “Medical History and Previous surgical procedures” page of the eCRF will be assigned to prior or concomitant.

See APPENDIX 2 for handling of partial dates for medical history, surgeries and procedures; if it is not possible to define a history, surgery or procedure as prior, concomitant, or post-treatment, it will be classified by the worst case; i.e., concomitant.

- Prior medical history, surgeries, and procedures are defined as those conditions or procedures which stop prior to or at Screening.
- Concomitant medical history, surgeries, and procedures are defined as those conditions or procedure which:

Document: \\ieedc-
vnasc01\BIOSdata\Boehringer_Ingelheim\BI_695501\NVA96252\Biostatistics\Documentation\S
AP\BI1297.4 SAP FINAL v4.0_22MAY2019.docx

Author: Version Number: Final V4.0
Version Date: 22MAY2019

Template No: CS_TP_BS016 Revision 5
Effective Date: 01Apr2018

Reference: CS_WI_BS005

- started prior to or at Screening and are ongoing or active at the date of Screening
- or
- started after Screening during the treatment period.

Prior and concomitant surgical and medical history will be presented by SOC and PT (Preferred Term) in two separate tables.

12. MEDICATIONS

Medications will be presented at Primary Analysis for the SAF, at Final Analysis for the FAS and SAF. They will be coded using the WHO Drug Dictionary (WHO-DD) version SEP2016 or higher.

No ATC class coding will be performed. The medical terms will be summarized by WHO-DD Preferred Name. The WHO-DD Preferred Name will be sorted by decreasing frequencies.

See APPENDIX 2 for handling of partial dates for medications, in the case where it is not possible to define a medication as prior, concomitant, or post treatment, the medication will be classified by the worst case; i.e., concomitant.

- ‘Prior’ medications are medications which started and stopped prior to the first dose of trial medication.
- ‘Concomitant’ medications are medications which:
 - started prior to, on, or after the first dose of trial medication and started no later than end of trial medication,
 - AND ended on or after the date of first dose of trial medication or were ongoing at the end of the trial.
- ‘Post’ medications are medications which started after the last dose of trial medication.

Prior, concomitant, and post medications will be presented in separate tables.

13. TRIAL MEDICATION EXPOSURE

Exposure to trial medication will be presented at Primary Analysis for the SAF, at Final Analysis for the FAS and

Document:	\\ieedc-vnasc01\BIOSdata\Boehringer_Ingelheim\BI_695501\NVA96252\Biostatistics\Documentation\SAP\BI1297.4 SAP FINAL v4.0_22MAY2019.docx		
Author:	Version Number:	Final V4.0	
	Version Date:	22MAY2019	
Template No: CS_TP_BS016	Revision 5	Reference:	CS_WI_BS005
Effective Date:	01Apr2018		

SAF.

The proportion of subjects treated at each planned visit (administration on Day 1 and every other week until Day 323) and per treatment group will be presented.

Descriptive statistics for the number of injections from Day 1 up to Week 4 (included) and from Week 4 (excluded) up to Week 46 per subjects will be presented.

Number of subjects per duration of exposure categories, patient time (years) per duration of exposure categories, and descriptive statistics for duration of exposure will be presented.

Exposure categories will be the following cumulative categories: ≥ 1 day, ≥ 2 weeks, ≥ 4 weeks, ≥ 12 weeks, ≥ 16 weeks, ≥ 24 weeks, ≥ 48 weeks.

13.1. DERIVATIONS

The date of first and last trial medication administration will be taken from the eCRF page "Trial Medication Injection".

Duration of exposure (days) = (date of last injection - date of first injection + 1).

Duration of exposure (weeks) = Duration of exposure (days)/7.

Patient Year Exposure (year) = cumulative duration of exposure in days per subject/365.25.

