19, 20, 23, 24, Visit¹ EoT² SFU² 14 15 16 17 18 22 21 25 34, 36, 42, 44, Week 24 28 40 48 26 30 32 56 38 46 239, 253, 295, 309, Day 169 183 197 211 225 281 337 393 267 323 Permitted visit window ±3 ±3 ±3 ±3 ±3 ±3 ±3 ±3 ±3 +7 (davs) LABS/SAFETY ASSESSMENTS TB testing (IGRA) Х Х CRP/fecal calprotectin Х Х Х Pregnancy test³ Х Х Х Х Physical examination Х Х Х (incl. weight) Х Vital signs⁴ Х Х Х Х Х Laboratory tests (serum chemistry, hematology, Х Х Х Х Х urinalysis) 12-lead electrocardiogram Х Х Х Previous and concomitant Х Х Х Х Х Х therapy Adverse events⁵ Х Х Х Х Х Х **EFFICACY ASSESSMENTS** CDAI evaluation⁶ Х Х Endoscopy (mucosal \mathbf{X}^7 ulceration, SES-CD)

FLOW CHART B: MAINTENANCE PERIOD (CONT'D)

TRIAL MEDICATION									
Contact IRT ⁹	Х	Х	Х	Х	Х	Х	Х	Х	
Switch from EU-approved Humira to BI 695501 ¹⁰	Х								
Trial medication administration ¹¹	Х	Х	Х	Х	Х	Х	Х	Х	

⁶ CDAI determination: exclude the day of bowel preparation for colonoscopy due to misleading impact on assessment of pain and liquid stool frequency. Patients will be required to complete a CDAI diary (provided at the previous visit) for the last 7 days prior to CDAI evaluation. At Visit 8 (Week 12), the hematocrit value from the central laboratory assessment at Visit 6 (Week 8) will be used to determine CDAI score. At visits where no physical examination is preformed, weight must be measured for use in CDAI determination.

⁷ Only applicable for patients who complete the 48-week treatment period

⁹ IRT will be contacted prior to every trial medication administration visit.

¹⁰ At Week 24, all patients on EU-approved Humira will switch to BI 695501.

Boehringer Ingelheim		12 Dec 2017
BI Trial No.: 1297.4		
c09542349-05	Trial Protocol	Page 12 of 93

¹¹ Trial medication should be administered every 2 weeks (±1 day up to Visit 4 and ±3 days from Visit 5 onwards). Patients will receive each dose of trial medication at the trial site until Week 22, trial medication will be administered by suitably qualified, designated unblinded trial personnel (Third party blinding); for remaining doses (Week 24 onwards), any suitably trained trial personnel may administer the trial medication since all patients will be receiving BI 695501. The last dose of BI 695501 will be at Week 46 for patients who remain on treatment throughout the trial. All assessments and procedures should be performed prior to trial medication administration, unless otherwise stated.

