6. INVESTIGATIONAL PLAN

6.1 **VISIT SCHEDULE**

A schedule of assessments is provided in Flow Chart A and Flow Chart B.

Visits will be scheduled as close as possible to the preplanned schedule:

- A visit window of -1/+2 days is permitted for Visit 2 (Day 1)
- A visit window of ± 1 day is permitted for Visit 3 to Visit 4
- A visit window of ± 3 days is permitted for Visit 5 to Visit 25, and EoT
- A visit window of +7 days is permitted for safety follow-up Visit
- Trial medication will be administered every 2 weeks (±1 day up to Visit 4 and ±3 days from Visit 5 onwards).

On trial medication administration days, all assessments should be performed prior to administration, unless otherwise specified. Laboratory samples must be drawn prior to trial medication injection.

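### The ≥ 48 weeks exposure category cannot be reached under the SAP's own duration formula: an on-schedule completer scores 46.1 weeks

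*SAP*

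**What the plan says.** SAP 13.1 defines duration as "Duration of exposure (days) = (date of last injection - date of first injection + 1", converts it by "Duration of exposure (weeks) = Duration of exposure (days)/7", and uses the same days for patient time: "Patient Year Exposure (year) = cumulative duration of exposure in days per subject/365.25".

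SAP 13 plans a table of subjects and patient-years by cumulative duration category, and the list ends with "≥ 16 weeks, ≥ 24 weeks, ≥ 48 weeks". The same section describes dosing as "administration on Day 1 and every other week until Day 323". Protocol Flow Chart B, footnote 11, agrees: "The last dose of BI 695501 will be at Week 46 for patients who remain on treatment throughout the trial".

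On timing, Protocol 6.1 states "A visit window of -1/+2 days is permitted for Visit 2 (Day 1") and gives a ±3-day window that "is permitted for Visit 5 to Visit 25, and EoT". The Week 46 dose is Visit 25.

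SAP 9 separately counts patients who completed treatment at Day 337 (Week 48), in line with the protocol's 48-week treatment period.

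**The concern.** The formula stops the clock on the day of the last injection, two weeks before the Week 48 end-of-treatment visit. The top category is set as though the clock ran to Week 48. Both rules are in SAP 13, and they cannot both describe a completer.

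Followed as written, the exposure table will have a top row of about 0% with no patient-time, while the disposition table reports a number of Week 48 completers. The row meant to show how many patients had the full course would carry no information. The next row down, ≥ 24 weeks, would combine completers with everyone who stopped after the switch.

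**Working it through.** **Inputs.** Duration formula and weeks conversion: SAP 13.1. First and last planned doses, Day 1 and Day 323: SAP 13. Windows of −1/+2 days at Visit 2 and ±3 days at Visit 25: Protocol 6.1. Top category of ≥ 48 weeks: SAP 13.

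**Step 1: the last dosing day.** Week 46 is Day 46 × 7 + 1 = 323, which reproduces the SAP's own day. Week 44 is Day 44 × 7 + 1 = 309.

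**Step 2: duration under the SAP formula.**

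| Patient | Days | Weeks |
|---|---|---|
| Completer, on schedule | 323 − 1 + 1 = 323 | 46.1 |
| Completer, longest within windows (first dose 1 day early, last 3 days late) | 326 − 0 + 1 = 327 | 46.7 |
| Completer, shortest within windows (first dose 2 days late, last 3 days early) | 320 − 3 + 1 = 318 | 45.4 |
| Last dose at Week 44, longest within windows | 312 − 0 + 1 = 313 | 44.7 |

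For the window extremes, days are counted on the nominal visit calendar, so a first dose one day early falls on day 0.

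**Step 3: what ≥ 48 weeks needs.** 48 × 7 = 336 days. With a first dose on Day 1, the last injection would have to fall on Day 336 or later. That is 336 − 323 = 13 days late, and 336 − 326 = 10 days beyond the window.

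**Step 4: the lower categories.** On schedule, the doses at Weeks 2, 4, 12, 16 and 24 fall on Days 15, 29, 85, 113 and 169, giving 2.14, 4.14, 12.14, 16.14 and 24.14 weeks. Each lower category therefore nominally means that the dose due at that week was given. The margin is one day: a Week 24 dose given 3 days early yields 166 days, or 23.7 weeks. Only the top label fails outright.

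**Step 5: a top label that works.** ≥ 45 weeks is 315 days. The shortest within-window completer (318) is in, and the longest within-window patient last dosed at Week 44 (313) is out.

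**Step 6: the alternative definition.** Counting the last dosing interval (last − first + 14) gives an on-schedule completer 323 − 1 + 14 = 336 days, or 48.0 weeks. The shortest within-window completer gets 320 − 3 + 14 = 331 days (47.3 weeks). The longest within-window patient last dosed at Week 44 gets 312 − 0 + 14 = 326 days (46.6 weeks). A ≥ 47 weeks label (329 days) separates the two. The lower cut-offs then go wrong:
- A single injection counts as 14 days, so ≥ 2 weeks becomes nearly the same row as ≥ 1 day.
- A last dose at Week 22 gives 155 − 1 + 14 = 168 days, or 24.0 weeks, and counts as ≥ 24 weeks without the Week 24 dose.
- On-schedule patients sit exactly on the cut-offs, so one day early drops them a category.

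**The case against.** The strongest reply is that first-to-last-injection is a usable, explicitly stated convention. Nothing in either document defines exposure to include an interval after the last dose. That stands. The formula is not an error in itself, and it fits the lower categories nominally.

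A reader might infer that patient-years are understated. A completer has 323/365.25 = 0.884 patient-years, against 336/365.25 = 0.920 if 14 days are added. That shortfall exists only relative to the second definition, which the SAP does not adopt. The difference is the same 13 days for every patient and larger only as a proportion in early discontinuers.

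A reader might also quote a 46% loss for Week 4 non-responders (15 days against 28). The documents do not settle this. Protocol 4.1.4 says that each patient receives a Week 4 dose, and also that non-responders receive no further trial medication. Flow Chart A marks dosing at three visits and places safety follow-up on Day 99, which is 29 + 70. Under the current formula the duration is 15 or 29 days, depending on the reading.

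Nor would the table lead a careful reader to conclude that nobody completed. SAP 13 also reports the proportion treated at each planned visit to Day 323, and SAP 9 reports completion.

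Finally, the category is not strictly impossible. A last injection at least 13 days late would reach it. So could a reading of ±3 days as a tolerance on each interval that accumulates, although Protocol 6.1 attaches the windows to visits. None of this makes the row reachable for a patient dosed within those windows.

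**Conclusion.** The point holds as an internal mismatch between one category label and the formula that feeds it. The on-schedule maximum is 46.1 weeks, and the range within the windows is 45.4 to 46.7 weeks, so the ≥ 48 weeks row and its patient-time will be about zero in both arms. This assumes windows measured around the scheduled visit days.

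The consequence is limited to exposure reporting. The visible adverse event comparisons use subject counts, risk ratios and risk differences. Treatment emergence uses its own window of 70 days after the last dose. Efficacy does not use exposure duration. The documents do not support a wider claim that safety rates or arm comparisons are biased.

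**What to change.** Keep the SAP 13.1 formula and relabel the top category in SAP 13 as ≥ 45 weeks. Add one sentence stating that exposure and patient-years run from first to last injection and exclude the dosing interval after the last injection. The cost is one label, one sentence and the matching table shell.

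If the sponsor prefers to count the last interval, use last − first + 14, cut at death, with a top category of ≥ 47 weeks, and reset the lower cut-offs at the same time. Changing the formula alone would move the uninformative row from the top of the table to the bottom.

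Separately, the passages on whether Week 4 non-responders receive the Week 4 dose (Protocol 4.1.4 and Flow Chart A) must be reconciled before any exposure figure is quoted for them.

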14. STUDY MEDICATION COMPLIANCE

Compliance to trial medication will be presented at Primary Analysis for the SAF, at Final Analysis for the FAS, and SAF.

14.1. DERIVATIONS

Compliance with trial medication will be based on the eCRF page "Trial Medication Injection". An administered injection is considered when the question "Was full dose given" is answered "Yes".

Compliance will be based on the comparison of actual administered injections and the planned usage. Compliance will include visits until treatment discontinuation.

- "Per visit" compliance will be calculated as follows:

Compliance (%) = 100% if the injection occurred at the specific visit

Document:	\\ieedc-vnasc01\BIOSdata\Boehringer_Ingelheim\BI_695501\NVA96252\Biostatistics\Documentation\SAP\BI1297.4 SAP FINAL v4.0_22MAY2019.docx		
Author:	Version Number:	Final V4.0	
	Version Date:	22MAY2019	
Template No:	CS_TP_BS016	Revision 5	Reference: CS_WI_BS005
Effective Date:	01Apr2018		

= 0% otherwise

Note: One administration is planned at each visit.

- “Overall” compliance will be calculated as follows:

Compliance (%) = (Number of administered injections)*100/Planned number of injections

- “Week 4” compliance will be calculated considering the injections until Week 4 (visit 4) (included).
- “Week 24” compliance will be calculated considering the injections until Week 24 (visit 14) (included).

